#### **10.1.3. Data Protection**

- Participants will be assigned a unique identifier by the investigator. Any participant records or datasets that are transferred to the sponsor will contain the identifier only; participant names or any information which would make the participant identifiable will not be transferred.
- The participant must be informed that his/her personal study-related data will be used by the sponsor in accordance with local data protection law. The level of disclosure must also be explained to the participant.
- The participant must be informed that his/her medical records may be examined by Clinical Quality Assurance auditors or other authorized personnel appointed by the sponsor, by appropriate IRB/IEC members, and by inspectors from regulatory authorities.

#### **10.1.4. Dissemination of Clinical Study Data**

#### **10.1.5. Data Quality Assurance**

To ensure accurate, complete, and reliable data, the sponsor or its representatives will do the following:

- provide instructional material to the study sites, as appropriate
- provide sponsor start-up training to instruct the investigators and study coordinators. This training will give instruction on the protocol, the completion of the CRFs, and study procedures.
- make periodic visits to the study site

- be available for consultation and stay in contact with the study site personnel by mail, telephone, and/or fax
- review and verify data reported to detect potential errors

In addition, the sponsor or its representatives will periodically check a sample of the participant data recorded against source documents at the study site. The study may be audited by the sponsor or its representatives and/or regulatory agencies at any time. Investigators will be given notice before an audit occurs.

The investigator will keep records of all original source data. This might include laboratory tests, medical records, and clinical notes. If requested, the investigator will provide the sponsor, applicable regulatory agencies, and applicable ERBs with direct access to original source documents.

### **Data Capture System**

The investigator is responsible for ensuring the accuracy, completeness, legibility, and timeliness of the data reported to the sponsor.

An electronic data capture system (EDC) will be used in this study for the collection of CRF data. The investigator maintains a separate source for the data entered by the investigator or designee into the sponsor-provided EDC system. The investigator is responsible for the identification of any data to be considered source and for the confirmation that data reported are accurate and complete by signing the CRF.

Additionally, clinical outcome assessment (COA) data will be collected by the subject, via a paper source document and will be transcribed by the investigator site personnel into the EDC system.

Data collected via the sponsor-provided data capture system will be stored at third party. The investigator will have continuous access to the data during the study and until decommissioning of the data capture system. Prior to decommissioning, the investigator will receive an archival copy of pertinent data for retention.

Data managed by a central vendor, such as laboratory test data, will be stored electronically in the central vendor's database system and the results will be provided to the investigator for review and retention. Data will subsequently be transferred from the central vendor to the Lilly data warehouse.

Data from complaint forms submitted to Lilly will be encoded and stored in the global product complaint management system.

#### **10.1.6. Source Documents**

- Source documents provide evidence for the existence of the participant and substantiate the integrity of the data collected. Source documents are filed at the investigator's site.
- Data reported on the CRF or entered in the eCRF that are transcribed from source documents must be consistent with the source documents or the discrepancies must be explained. The investigator may need to request previous medical records or transfer records, depending on the study. Also, current medical records must be available.

**10.1.7. Study and Site Closure****10.1.7.1. Discontinuation of the Study**

The study will be discontinued if Lilly or its designee judges it necessary for medical, safety, regulatory, or other reasons consistent with applicable laws, regulations, and GCP.

**10.1.7.2. Discontinuation of Study Sites**

Study site participation may be discontinued if Lilly or its designee, the investigator, or the ERB of the study site judges it necessary for medical, safety, regulatory, or other reasons consistent with applicable laws, regulations, and GCP.

**10.2. Appendix 2: Clinical Laboratory Tests**

- The tests detailed below will be performed as indicated in the table below.
- Local laboratory results are required for inclusion/exclusion determination, study intervention administration, and/or response evaluation. If a local sample is required, it is important that the sample for central analysis is obtained at the same time. Additionally, if the local laboratory results are used to make either a study intervention decision or response evaluation, the clinically significant abnormalities must be entered into the AE CRF. If there is an abnormal laboratory value or abnormal value for any other diagnostic or screening test (for example, blood pressure increased, neutrophils decreased, etc.) and it is known to be related to a diagnosis (for example, hypertension, neutropenia, etc.) this should be reported in the CRF as an AE. Do not enter the test abnormality; enter the disease diagnosis or categorical term.
- Additional tests may be performed at any time during the study as determined necessary by the investigator or required by local regulations and clinically significant findings should be recorded reported in the CRF as an AE.

Enrollment and treatment decisions may be based upon local laboratory results. Discrepancies between local and central laboratory results will not be considered a protocol deviation.

**Clinical Laboratory Tests**

**Hematologya -local laboratory**

Leukocytes (WBC)	Basophils
Neutrophils	Erythrocytes (RBC)
Lymphocytes	Hemoglobin (HGB)
Monocytes	Hematocrit (HCT)
Eosinophils	Platelets (PLT)

**Coagulation -local laboratory**

PT/INR	PTT/aPTT
--------	----------

**Clinical chemistrya -local laboratory**

Serum concentrations of:

Alanine aminotransferase (ALT)	Calcium
Albumin	Creatinine
Alkaline phosphatase	Glucose (random)
Amylase	Lipase
Aspartate aminotransferase (AST)	Potassium
Bilirubin, direct	Protein
Bilirubin, total	Sodium
Blood urea nitrogen (BUN) or blood urea	

**Urinalysis -local laboratory**

Blood	Protein
Glucose	Specific gravity
Ketones	Urine leukocyte esterase d
pH	

[figure not shown]
**Pregnancy Testc -local laboratory**

Urine pregnancy test	Serum pregnancy test
----------------------	----------------------

Note: Urine pregnancy test at a minimum sensitivity of 25 IU/L or equivalent units of  $\beta$ -hCG. If urine pregnancy results cannot be confirmed as negative, a serum pregnancy test will be required

**Thyroid panel -local laboratory**

Triiodothyronine (T3) or Free Triiodothyronine (FT3)	Thyroid-stimulating hormone (TSH)
Free Thyroxine (FT4)	

**Tumor markers -local laboratory**

PSA	CA-125
CEA	CA 19-9

**IHC - Central laboratory**

CD73 expression for Phase 1b Cohort C

Selected tests may be obtained in the event of anaphylaxis or generalized urticaria.

**Hypersensitivity Testsb – Central laboratory**

Anti-LY antibodies (immunogenicity)	Basophil Activation Test
LY concentration (PK)	Complements
Tryptase	Cytokine Panel
N-methylhistamine	

Abbreviations: aPTT = activated partial thromboplastin time; CA-125 = cancer antigen 125; CA 19-9 = cancer antigen 19-9; CEA = carcinoembryonic antigen; CRF = case report form; hCG = human chorionic gonadotropin; HCT = hematocrit; HGB = hemoglobin; INR = international normalized ratio; MB = muscle and brain; PLT = platelets; PK = pharmacokinetics; PT = prothrombin time; PTT = partial thromboplastin time; PSA = prostate specific antigen; RBC = red blood cells; WBC = white blood cells.

a Treatment and enrollment decisions will be based on local laboratory results.

Note: Neutrophils reported by automated differential hematology instruments include both segmented and band forms. When a manual differential is needed to report the neutrophils, the segmented and band forms should be added together and recorded on the CRF, unless the CRF specifically provides an entry field for bands.

b Central laboratory. In addition, local labs may be collected at investigator’s discretion.

c For female patients of childbearing potential.

d Urine microscopy may be used in place of the urine leukocyte esterase assessment to test for the presence of WBC.

### **10.3. Appendix 3: Contraceptive Guidance and Collection of Pregnancy Information**

#### **Definitions:**

#### **Woman of Childbearing Potential (WOCBP)**

A woman is considered fertile following menarche and until becoming post-menopausal unless permanently sterile (see below).

If fertility is unclear (e.g., amenorrhea in adolescents or athletes) and a menstrual cycle cannot be confirmed before first dose of study intervention, additional evaluation should be considered.

Women in the following categories are not considered WOCBP

1. Premenarchal
2. Premenopausal female with 1 of the following:
  - a. Documented hysterectomy
  - b. Documented bilateral salpingectomy
  - c. Documented bilateral oophorectomy

For individuals with permanent infertility due to an alternate medical cause other than the above, (e.g., mullerian agenesis, androgen insensitivity), investigator discretion should be applied to determining study entry.

Note: Documentation can come from the site personnel's: review of the participant's medical records, medical examination, or medical history interview.

3. Postmenopausal female
  - A postmenopausal state is defined as no menses for 12 months without an alternative medical cause.
  - A high follicle stimulating hormone (FSH) level in the postmenopausal range may be used to confirm a postmenopausal state in women not using hormonal contraception or hormonal replacement therapy (HRT). However, in the absence of 12 months of amenorrhea, confirmation with more than 1 FSH measurement is required.
  - Females on HRT and whose menopausal status is in doubt will be required to use one of the non-estrogen hormonal highly effective contraception methods if they wish to continue their HRT during the study. Otherwise, they must discontinue HRT to allow confirmation of postmenopausal status before study enrollment.

#### **Contraception Guidance:**

1. Women of child-bearing potential who are abstinent (if this is complete abstinence, as their preferred and usual lifestyle) or in a same sex relationship (as part of their preferred and usual lifestyle) must agree to either remain abstinent or stay in a same sex relationship without sexual relationships with males. Periodic abstinence methods (e.g., calendar, ovulation, symptothermal, post-ovulation methods), declaration of abstinence for the duration of a trial, and withdrawal) are not acceptable methods of contraception.

2. Women of child-bearing potential must use 2 effective methods of contraception for the entirety of the study. Abstinence or contraception must continue following completion of study drug administration, LY3475070 and pembrolizumab, for at least 120 days following the last dose of study drugs or country requirements, whichever is longer. For patients receiving LY3475070 only, contraception should be maintained for 5 half-lives or until plasma concentrations are equal to 1/25th of the nonclinical NOAEL exposure, (NOAEL/25) predicted to be 7 days.
  - a. Women of child-bearing potential participating must test negative for pregnancy prior to initiation of treatment as indicated by a negative urine pregnancy test at the screening visit followed by a negative serum pregnancy test within 24 hours prior to study drug exposure. Pregnancy testing is conducted at monthly intervals during study treatment in both treatment arms, and up to 120 days after study discontinuation for patients receiving LY3475070 and pembrolizumab, and at 7 days after study discontinuation for patients receiving LY3475070 monotherapy.
  - b. Two effective methods of contraception, such as male or female condoms with spermicide, diaphragms with spermicide or cervical sponges, will be used. The subject may choose to use a double barrier method of contraception. Barrier protection methods without concomitant use of a spermicide are not a reliable or acceptable method. Thus, each barrier method must include use of a spermicide. It should be noted that the use of male and female condoms as a double barrier method is not considered acceptable due to the high failure rate when these methods are combined.
    - i. One of the 2 methods of contraception must be a highly effective (less than 1% failure rate) method of contraception, such as combination oral contraceptives, implanted contraceptives or intrauterine devices.

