## Cohort E: Patients with mTNBC

- g) Prior PD-1/L1 inhibitor therapy allowed;
- h) Patients must have received treatment for metastatic disease (at least 1 regimen of cytotoxic chemotherapy for metastatic disease);

Participants are eligible to be included in the study only if **all** of the following criteria apply:

8. Must be able to provide informed consent, as described in Appendix 1, which includes compliance with the requirements and restrictions listed in the informed consent form (ICF) and in this protocol, according to local regulations and are at least 18 years of age.
9. Men with partners of childbearing potential must use a condom during intercourse. Men with partners of childbearing potential or women with childbearing potential must agree to use 2 effective methods of contraception including a highly effective contraceptive method of birth control (Appendix 3) during study treatment and for at least 120 days following the last dose of LY3475070 and pembrolizumab or country requirements, whichever is longer. For patients receiving LY3475070 only, contraception should be maintained for 7 days following the last dose. Additional guidance for contraception during and after study intervention are located in Appendix 3.
10. Women of childbearing potential must have a negative urine pregnancy test at the screening visit followed by a negative serum pregnancy test documented within 24 hours prior to initiation of treatment. If the screening urine test is positive or cannot be confirmed as negative, a serum pregnancy test will be required. Additional guidance for pregnancy testing during and after study intervention is located in Appendix 2 and Appendix 3.
11. Have at least 1 measurable lesion using standard techniques by RECIST version 1.1 (Eisenhauer et al. 2009). **Exception:** patients enrolled in the dose escalation phase and mCRPC patients enrolled in Cohort D1 and D2 are **not** required to have measurable disease.
12. Have a performance status (PS) of 0 or 1 on the Eastern Cooperative Oncology Group (ECOG) scale (Oken et al. 1982).
13. Previous treatments: Have discontinued all previous treatments for cancer and recovered from the acute effects of therapy (except alopecia). Patients must have discontinued from previous treatments, as shown below:

Previous Treatment	Length of Time Prior to First Dose of LY3475070
Endocrine therapies	$\geq 14$ days

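### Appendix 3 item 2b permits a double barrier method, which does not fit its own sub-item (i) or Inclusion Criterion 9, both of which require one of the two methods to be highly effective

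*Protocol*

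**What the plan says.** The relevant text is in two places in the protocol.

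Appendix 3 (Section 10.3, Contraception Guidance), item 2, sets the general duty: "Women of child-bearing potential must use 2 effective methods of contraception for the entirety of the study". Item 2b describes the methods: "Two effective methods of contraception, such as male or female condoms with spermicide, diaphragms with spermicide or cervical sponges, will be used". Every example there is a barrier method. Item 2b then gives an express permission: "The subject may choose to use a double barrier method of contraception". It sets two limits. Each barrier must be used with a spermicide, and one pairing is ruled out: "It should be noted that the use of male and female condoms as a double barrier method is not considered acceptable". Sub-item 2b(i) follows: "One of the 2 methods of contraception must be a highly effective (less than 1% failure rate) method of contraception". Its examples are oral contraceptives, implants and intrauterine devices.

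Section 5.1, Inclusion Criterion 9, says that patients to whom it applies "must agree to use 2 effective methods of contraception including a highly effective contraceptive method of birth control", and refers to Appendix 3. It describes that appendix as a source of further guidance. The period covered is study treatment plus at least 120 days after the last dose for the combination (longer if a country requires it), or 7 days for LY3475070 alone.

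**The concern.** Item 2b uses barrier methods to show what the two methods are and then lets the patient choose a double barrier. Read alone, it tells site staff that two barriers are enough. Sub-item (i) and Inclusion 9 say that one of the two must be highly effective. Inclusion 9 points to Appendix 3, so staff meet the permissive sentence exactly where they are sent when counselling a patient.

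A site that relies on that sentence could enrol and dose a woman who does not meet Inclusion 9. The opening of Section 5 rules out waivers of enrolment criteria. Under Section 7.2.1 an inadvertently enrolled patient should stop study treatment, unless continuing is medically necessary and the sponsor's physician approves. Appendix 7 gives the UK version without that exception. The stakes are therefore an eligibility deviation, possible loss of study treatment for that patient, and possible fetal exposure to a first-in-human drug, alone or with pembrolizumab.

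**Working it through.** There is no figure to reproduce and no arithmetic applies. The check is whether one pair of methods can satisfy every line. Both opposing provisions stand in the current protocol text.

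Three pairs, tested against the three statements:

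| Two methods used | Item 2b | Sub-item 2b(i) | Inclusion 9 |
|---|---|---|---|
| Diaphragm with spermicide + male condom with spermicide | Met: both are on its list, and the pairing is not excluded | Not met on the listed examples | Not met on the same basis |
| Intrauterine device + male condom with spermicide | Met | Met | Met |
| Intrauterine device + double barrier, counted as one method | Met | Met | Met |

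The first row is the problem. It is what the permissive sentence most naturally describes.

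There are three ways to read the double-barrier sentence:

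1. The double barrier is the two methods. The sentence then conflicts with 2b(i) and Inclusion 9, unless a barrier method used with spermicide has a failure rate below 1%. The documents do not say that it does.
2. Sub-item (i) qualifies item 2b. At most one of the two methods can then be a barrier (on the same footing), and the permission has nothing left to permit.
3. The double barrier counts as one method and a highly effective method is added. All lines are then satisfied, but the text does not say this. Item 2b uses barriers to illustrate the two methods and treats a double barrier as two barriers combined.

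Only the third reading gives the sentence a function without conflict, and it has to be supplied by the reader.

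The figure of less than 1% appears only in Appendix 3. Inclusion 9 says highly effective and reaches the figure through its cross-reference.

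**The case against.** The strongest reply is that sub-item (i) is nested under item 2b and should be read with it. The double-barrier sentence is permissive and sub-item (i) is mandatory. Taken together, barriers are acceptable provided that one of the two methods is highly effective. A careful site may well read it so, and Inclusion 9 supports that outcome. This stands in part: it limits the likely harm, but it leaves the permission either empty or dependent on an unstated third product.

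A reader might infer more than the text supports, in three ways.

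- *That the protocol has two competing eligibility rules and nothing to choose between them.* It does not. Section 5.1 sets eligibility, Inclusion 9 is clear, and the appendix is offered as guidance. The two mandatory statements agree; the sentence out of line is permissive.
- *That two barriers can never meet sub-item (i).* The documents give no failure rate for a double barrier with spermicide, and the list of highly effective methods is illustrative. What they do show is that no barrier is among the examples of highly effective methods.
- *That every woman of childbearing potential is affected.* Item 1 of the Contraception Guidance deals separately with abstinent women and women in same-sex relationships, and women already using a highly effective method are unaffected.

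The risk also has to be weighed against other safeguards: a urine test at screening, a serum test within 24 hours before treatment, monthly testing on treatment, testing afterwards, and discontinuation of treatment on pregnancy. These detect pregnancy and limit exposure; they do not resolve the wording.

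**Conclusion.** The point holds as an internal inconsistency in the contraception guidance. Item 2b offers an option that, used as the two required methods, does not satisfy sub-item (i) or Inclusion 9 on the document's own examples.

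Its reach is narrow. It concerns women of childbearing potential in Phase 1a and in Cohorts C and E (Cohort D enrols men) who propose barrier-only contraception, at a site that relies on the permissive sentence and overlooks the two mandatory ones. The documents do not give their number. Each such woman would be an eligibility deviation under Inclusion 9, provided that barrier methods do not count as highly effective. That is the assumption on which the conclusion rests; it follows from the examples given and not from any stated failure rate.

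No endpoint, analysis population, sample size or estimate is affected. The inconsistency should be corrected because it bears on eligibility and possible fetal exposure and is cheap to remove.

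**What to change.** Reconcile the double-barrier sentence and the barrier-only examples in Appendix 3 item 2b with sub-item 2b(i) and Inclusion 9, so that no option listed in one place fails another. If a double barrier is meant to count as one of the two methods, the text should say so; if not, the statement that is not intended should be amended or removed. Which clinical rule is right is for the sponsor to decide.

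The consent form should be checked against the reconciled wording. The consent pages were not available for this review, so no discrepancy there is alleged.

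The cost is a short wording change at the next amendment, mainly in one appendix item, with no added procedures. If the check leads to a revised consent form, Appendix 1 (Section 10.1.2) requires current participants to be re-consented to it.

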### **Collection of Pregnancy Information**

#### **Male participants with partners who become pregnant**

- The investigator will attempt to collect pregnancy information on any male participant's female partner who becomes pregnant while the male participant is in this study.
- After obtaining the necessary signed informed consent from the pregnant female partner directly, the investigator will record pregnancy information on the appropriate form and submit it to the sponsor within 24 hours of obtaining informed consent from the pregnant female partner. The female partner will also be followed to determine the outcome of the pregnancy. Information on the status of the mother and child will be forwarded to the sponsor. Generally, the follow-up will be no longer than 6 to 8 weeks following the estimated delivery date. Any termination of the pregnancy will be reported regardless of fetal status (presence or absence of anomalies) or indication for the procedure.

